Section 6.4 Clarification of how SAEs will be reported after the FPV.	This confirms that SAEs will still be reported via the standard pharmacovigilance process even after the FPV.
Table 11 AZD1775 dose modifications for QTc interval prolongation has been updated per most recent PSSR.	This aligns the CSP with the most current PSSR guidelines.
Version 4.0, 6 April 2017	
Changes to the protocol are summarized below:	Rationale
Throughout document: The dose expansion of the study design (Part B) has been removed. A QD 5/2 weekly dosing schedule has been added to the study	The focus of the study has been returned to determining the correct dose level and dosing schedule
Throughout the document: The number of patients to be enrolled on the study has been revised.	To accurately reflect the number of patients to be enrolled after removal of Part B and addition of the QD 5/2 weekly dosing schedule.
Throughout the document: Introduction of new printed capsule formulation AZD1775 strengths (50mg, 75mg and 100mg) in addition to the existing plain capsule formulation AZD1775 strengths (25mg and 100mg).	A new drug formulation has been added and guidance on use of the formulation has been provided
Table 3, Table 4, Table 6, Section 5.4.1, and Section 6.7: Additional PK sample collections were added when imaging is performed for response assessment, at the time of AEs possibly related to AZD1775 (unless the last dose of study drug was administered > 1 week prior to the event), and at the end of	To provide more PK information to the study.

treatment or at the time of progression.
	

Figures 1 -4, Table 4 and throughout the document:
 
The study design (Figures 1 and 3) has been updated and the treatment cohorts are shown in Table 1.
 
Dosing schedules for every cohort have been added in Figure 2 (BID Dosing Cohorts) and Figure 4 (QD Dosing Cohorts)
 
Study Plan and Assessments for the QD 5/2 Schedule (Table 4) has been revised to include QD 5/2 weekly dosing
 
The AZD1775 dosing cohorts table (Table 12) has been revised to show each dosing cohort.
	
These revisions were made to provide clarity for the investigational sites and investigators.

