1.2.3 Safety

Based on the safety data from the completed AZD1775 clinical studies and preliminary data from ongoing studies, adverse drug reactions to AZD1775 monotherapy include: anaemia, neutropenia, thrombocytopenia, QTc prolongation, gastrointestinal events such as dyspepsia, diarrhoea, nausea and vomiting (with or without dehydration or serum electrolyte decreases), as well as decreased appetite.

Based on information emerging during the clinical development programme of AZD1775, potential risks with AZD1775 monotherapy include asthenia/fatigue, febrile neutropenia, gastrointestinal haemorrhage, lymphopenia/lymphocyte count decreased, leukopenia/WBC count decreased, pancytopenia, myalgia, stomatitis, sepsis and transaminases elevation.

Refer to the IB for AZD1775 for information on the potential benefits and assessment of potential and known risks.

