4.3.2.3 Final Protocol Visit and Beyond

The Final Protocol Visit (FPV) requirement applies only to patients who continue AZD1775 after the implementation of the Clinical Study Protocol (CSP) Version 5. Patients should return to the clinic soon after the CSP Version 5 is implemented in order to be re-consented on the associated updated ICF.

Beyond the FPV, patients may continue to receive AZD1775 if they are deriving clinical benefit, in the opinion of the Investigator, and not fulfilling any of the discontinuation criteria. Such patients are to be treated in accordance with local practice and as deemed appropriate by the Investigator to ensure continued safety monitoring of the patient while receiving the investigational product. It is recommended to continue observing ongoing patients at the frequency indicated within the study plans as described in [Table 3](#) and [Table 4](#). Restrictions regarding concomitant medications (refer to Section [7.8.2](#)) will be followed while the patient is receiving AZD1775. A change in AZD1775 dose/schedule should only occur for safety reasons, based on the Investigator's judgement, and should generally follow the approach for dose reduction and discontinuation as described in this protocol. Combining AZD1775 with other anti-cancer therapy is not allowed.

If a patient is no longer receiving benefit from AZD1775 beyond the FPV in the opinion of the treating physician, then the study drug should be stopped. The Investigator will inform AstraZeneca when a patient discontinues the study drug. Patients must return unused medication during routine clinic visits, and drug accountability information must continue to be collected in patient source documents until the patient discontinues treatment. In addition, provided that a patient gives proper informed consent, a plasma isolation (ctDNA) blood sample for future biomedical research should be obtained at the time of AZD1775 discontinuation, if due to disease progression. Patients will continue to be monitored for all SAEs, pregnancies, and overdoses for 30 days after the last dose of the investigational product.

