5.2.3 Electrocardiogram

Triplicate 12-lead safety ECGs (paper ECG printout of 10 seconds for Investigator review) will be taken at screening and prior to dosing on Day 1 of each cycle (see [Table 2](#), [Table 3](#), and [Table 4](#)).

4, and Section 3.2). Triplicate ECGs should also be obtained to coincide with the non-food and food effect PK collections described in Table 2, Table 3 and Table 4. The triplicate ECG assessments must be performed before the PK sample is collected.

Triplicate ECG recordings should be taken within an approximate 5-minute period. QTc interval will be calculated using the Fridericia formula (per institutional standards) obtained from the 3 ECGs performed 2-5 minutes apart at study entry.

Additional ECGs may be taken at any other time the Investigator deems necessary for safety during the administration period. The patients will rest for at least 10 minutes before the start of each recording and they must be in the same supine body position (maximum 30 degrees flexion in the hip and feet not in contact with the footboard) at the recording time point.

The Investigator will judge the overall interpretation as normal or abnormal. If abnormal, it will be decided as to whether or not the abnormality is clinically significant or not clinically significant. The paper copy of each ECG reading will be retained with the patient's completed source documents. Only overall evaluation (normal/abnormal) will be recorded in the eCRF. If there is a clinically significant abnormal unscheduled ECG finding during the treatment period, this should be recorded on the AE eCRF, according to standard AE collection and reporting processes (see Section 6.3).

Attention should be paid to any detected increases in QTc interval. Patients who develop a single resting value of QTc interval of >450 msec/male and >470 msec/female or a shift from baseline of 60ms should stop taking AZD1775. Dosing can be resumed at a reduced dose (see section 6.7.3) after return of the resting QTc interval to pre-treatment status has been confirmed and correction of possible electrolyte imbalance has been made.

Monitoring of QTc, checking and correction of abnormal electrolyte levels and renal function are advised, especially in case of severe/prolonged diarrhoea. If QTc increases markedly from baseline, but stays below the above limits, a cardiologist's advice should be sought.

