6.7.3 Non-haematologic toxicity dose modifications

Substantial acute toxicities should be managed as medically indicated and with temporary suspension of investigational product, as appropriate. Dose reductions or holds and initiation of supportive care are allowed as clinically indicated by the treating physician.

Dose reductions of AZD1775 should be considered if the toxicity is considered to be related to AZD1775. Dose re-escalation is not permitted.

In general, if a patient experiences a G1/G2 non-haematological toxicity, no dose modification is required (except QTc prolongation, see table below). If a patient experiences a G3 or G4 toxicity which is not attributable to the disease or disease-related processes under investigation, dosing will be interrupted and/or the dose reduced, and supportive therapy administered as required. Any patient who develops a Grade 3 or 4 non-haematologic toxicity that does not resolve to \leq Grade 1 within 21 days should be removed from the study treatment unless approved by the Medical Monitor.

Table 11 AZD1775 dose modifications for QTc interval prolongation

Electrocardiogram QT corrected interval prolonged	
QTc Value	AZD1775

Table 11 AZD1775 dose modifications for QTc interval prolongation

Electrocardiogram QT corrected interval prolonged	
QTc 450-480 ms (males) or 470-480 ms (females)	Hold. Once QTc interval has returned to pretreatment status and correction of possible electrolyte imbalance has been made, resume at next lower dose level.
QTc 481-500 ms	Hold. Seek cardiologist advice, patient may resume at next lower dose level if cardiologist agrees.
QTc \geq 501 ms	Discontinue treatment. Seek cardiologist advice.
Shift from baseline of \geq 60ms	Discontinue treatment. Seek cardiologist advice.

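### Section 5.2.3 lets AZD1775 be resumed after a 60 ms QTc shift from baseline, while Table 11 requires discontinuation; Table 11 should govern

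*Protocol*

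**What the plan says.** Section 5.2.3 (Electrocardiogram) sets two triggers for stopping: a single resting QTc above 450 ms in men or 470 ms in women, or a shift from baseline. Of the second it says "or a shift from baseline of 60ms should stop taking AZD1775. Dosing can be resumed at a reduced dose". It refers to Section 6.7.3 for the reduced dose and allows resumption "after return of the resting QTc interval to pre-treatment status has been confirmed and correction of possible electrolyte imbalance has been made". It makes no exception for either trigger.

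Table 11 in Section 6.7.3 has four rows:

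- **450 to 480 ms (men) or 470 to 480 ms (women):** hold, then resume one dose level lower after recovery and electrolyte correction.
- **481 to 500 ms:** hold and consult a cardiologist; "patient may resume at next lower dose level if cardiologist agrees".
- **501 ms or more:** "Discontinue treatment. Seek cardiologist advice".
- **Shift from baseline of 60 ms or more:** the same instruction as for 501 ms or more.

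The Version 5.0 entry in the version history records that "AZD1775 dose modifications for QTc interval prolongation has been updated per most recent PSSR".

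**The concern.** An investigator whose patient shows a 60 ms shift finds two instructions. Both stop the drug at once. They differ on the next step: one permits re-exposure at a lower dose and the other does not. The protocol does not say which section takes precedence.

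What is at stake is patient safety. Section 1.2.3 states that "adverse drug reactions to AZD1775 monotherapy include: anaemia, neutropenia, thrombocytopenia, QTc prolongation" and goes on to other events. Section 5.2.3 itself notes that ondansetron, one of the two named options for the mandatory antiemetic, can rarely prolong QTc.

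The question remains live although enrolment is closed. Section 4.3.2.3 lets patients stay on AZD1775 beyond the final protocol visit provided they meet no discontinuation criterion, and says that dose changes "should generally follow the approach for dose reduction and discontinuation as described in this protocol". Whether a 60 ms shift is such a criterion is exactly what the two sections dispute.

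**Working it through.** No sample size, power or error rate is involved. The check compares the two texts and then works out when the conflict decides the outcome.

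**1. Same event, two actions.** For a 60 ms shift from baseline, 5.2.3 says stop, with resumption at a reduced dose possible after recovery. Table 11 says discontinue and consult a cardiologist.

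**2. Can the Table 11 instruction be read as a temporary stop?** No. The table uses hold in the two rows that allow resumption, and discontinue only for 501 ms or more and for the shift. The contrast in wording marks the shift row as one without resumption.

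**3. Does the cross-reference resolve it?** No. In 5.2.3 the reference to 6.7.3 is attached to the reduced dose, after the text has already said that dosing can resume. Followed for a patient with a shift, it leads to a row that offers no dose.

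**4. Which text is newer?** The version history records QTc guidance being added to 5.2.3 in Version 4 and Table 11 being updated in Version 5. The Version 5 entries list no matching change to 5.2.3. This suggests that 5.2.3 was not brought into line, but the conflict does not depend on that history.

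**5. When does the conflict decide the outcome?** QTc after the shift = baseline + shift. With a shift of exactly 60 ms, the shift is the only trigger when baseline is below 450 − 60 = 390 ms (men) or 470 − 60 = 410 ms (women). In whole milliseconds:

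| Baseline (ms) | QTc after +60 (ms) | Table 11 action on absolute QTc alone | Table 11 action on the shift |
|---|---|---|---|
| Men <390; women <410 | Men <450; women <470 | None | Discontinue |
| Men 390–420; women 410–420 | Men 450–480; women 470–480 | Hold, resume one level lower | Discontinue |
| 421–440 | 481–500 | Hold, resume if cardiologist agrees | Discontinue |
| ≥441 | ≥501 | Discontinue | Discontinue |

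For any baseline up to 500 − 60 = 440 ms, therefore, discontinuation after a shift of exactly 60 ms rests on the shift row alone, and 5.2.3 contradicts that row.

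**Example.** A man goes from 380 to 445 ms. The shift is 445 − 380 = 65 ms, which is at least 60 ms, and 445 ms is below the 450 ms limit. He may resume under 5.2.3 and is discontinued under Table 11.

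**6. Lesser gaps.** Section 5.2.3 states no upper QTc limit on resumption and omits the cardiologist's agreement needed at 481 to 500 ms; its reference to 6.7.3 partly covers both. Table 11 does not say that its shift row overrides its hold rows when both apply. The lower boundary also differs: 5.2.3 acts above 450 or 470 ms, while Table 11 starts at 450 or 470 ms.

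**The case against.** The strongest reply is that little harm is likely. Both texts stop the drug at once. Section 5.2.3 is permissive and conditional, and it sends the reader to the dose-modification section, where the shift row is explicit. An investigator who looks there before choosing a dose meets the stricter rule. All three schedules are closed to enrolment, the number of patients still on drug is not given, and after the final protocol visit treatment follows local practice and the investigator's judgement. The documents give no frequency of 60 ms shifts, and no endpoint or MTD rule has been shown to be affected.

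These points are fair and limit the likely number of patients affected. They do not remove the contradiction: an investigator who relies on 5.2.3 has written permission to re-expose a patient whom Table 11 takes off treatment.

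The reply is also right that the 481 to 500 ms and 501 ms rows are largely served by the cross-reference, that the lower boundary matters only at exactly 450 or 470 ms, and that calling the discontinuation permanent is an inference from the table's wording rather than its own term. These are secondary to the shift row.

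**Conclusion.** The concern holds. Two current safety instructions give opposite answers on re-exposure after a QTc shift of 60 ms or more. One of the four Table 11 rows is in firm conflict with 5.2.3; two more (481 to 500 ms, and 501 ms or more) are incomplete in 5.2.3 but partly covered by its cross-reference.

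The conclusion rests on reading discontinue in Table 11 as ending treatment, which the table's separate use of hold supports. How many patients would be affected cannot be estimated from the protocol. The point should still be corrected, because it concerns re-exposure to a drug with a listed QTc effect. Table 11 is the text to keep: it is graded, more cautious and more recently updated.

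**What to change.** Amend Section 5.2.3 so that, after the initial stop, all further action follows Table 11. In particular:

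- Allow resumption at the next lower dose level only if QTc was 500 ms or less and the shift was below 60 ms, after return to pre-treatment status and electrolyte correction, and with the cardiologist's agreement for 481 to 500 ms.
- Require permanent discontinuation for QTc of 501 ms or more or a shift of 60 ms or more, and write the 5.2.3 trigger as at least 60 ms.
- State in Table 11 that the shift row overrides the rows covering 450 to 500 ms.
- Use the same lower boundary in both places: above 450 ms in men and above 470 ms in women.

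Send a safety clarification to sites with patients still on drug.

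The cost is a text change to 5.2.3 and Table 11 and a letter to sites, with no new assessments. If the change is classed as substantial, Section 10.5 also requires a protocol amendment with ethics committee or IRB approval before implementation.

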5.2.4 Vital signs

Vital signs to be assessed include: resting heart rate, blood pressure, temperature and weight. Height will be measured at the screening visit only. Vital signs and weight should be obtained Day 1 of each treatment cycle (see Table 2, Table 3, and Table 4).

5.2.5 Tumour markers

An elevated tumour marker (e.g. CA-125, CEA, PSA, etc.) that is used by the investigator to monitor for tumour response will be collected at baseline, Day 1 of each cycle, and at the end of treatment. The results will be recorded in the eCRF. The tumour marker analysis will be performed by a local laboratory.

5.3 Other assessments

5.3.1 Patient reported outcomes

Not applicable.

5.4 Pharmacokinetics

5.4.1 Collection of samples for AZD1775 PKs

Pharmacokinetic samples for AZD1775 (2 mL) will be collected throughout the study as indicated below. The date and actual time of the PK sample is to be recorded in the medical records and eCRF. Samples will be obtained at the time points indicated in [Table 5](#) and [Table 6](#).

Table 5 Pharmacokinetic sampling schedule for food effect patients

Time relative to first dose in cycle	Cycle 1 Day 1	Cycle 1 Day 5	Cycle 2 Day 1	Cycle 5 Day 5 and then every 3-5 cycles thereafter ^a	At response assessment (+/- 24 hrs)	At time of AEs possibly related to AZD1775	At end of treatment or progression (+/- 24 hrs)
Pre-dose	X ^b	X ^b	X ^b	X ^b			
1 hour	X ^b	X ^b	X ^b	-			
2 hours	X ^b	X ^b	X ^b	-			
4 hours	X ^b	X ^b	X ^b	-			
6 hours	X ^b	X ^b	X ^b	-			
8 hours	X ^b	X ^b	X ^b	-			
10 hours	X ^b	X ^b	X ^b	-			
Unscheduled					X	X ^c	X

^a Beyond the PK for Cycle 5 Day 5, collections will be flexible and may be obtained once every 3, 4 or 5 cycles (instead of 4 cycles) on day 3, 4 or 5 (instead of day 5).

^b Triplicate ECGs should be obtained to coincide with the food effect PK collections. The triplicate ECG assessments will be performed before the PK sample is collected.

^c Unless the last dose of study drug was administered > 1 week prior to the event (See Section 6.7).

^d PK samples will no longer be required after implementation of CSP Version 5.

Table 6 Pharmacokinetic sampling schedule for non-food effect patients

Time relative to first dose in cycle	Cycle 1 Day 1	Cycle 1 Day 5	Cycle 5 Day 5	Cycle 6 Day 3, 4, or 5 then every 3-5 cycles thereafter^a	At response assessment (+/- 24 hrs)	At time of AEs possibly related to AZD1775	At end of treatment or progression (+/- 24 hrs)
Pre-dose	X ^b	X ^b	X ^b	X ^b			
1 hour	X ^b	X ^b	-				
2 hours	X ^b	X ^b	-				
4 hours	X ^b	X ^b	-				
6 hours	X ^b	X ^b	-				
8 hours	X ^b	X ^b	-				
10 hours	X ^b	X ^b	-				
24 hours	X ^{b,c}	X ^{b,c}					
Unscheduled					X	X ^d	X

- ^a Beyond the PK for Cycle 5 Day 5, collections will be flexible and may be obtained once every 3, 4 or 5 cycles (instead of every 4 cycles) on day 3, 4 or 5 (instead of day 5).
- ^b Triplicate ECGs should be obtained to coincide with the non-food effect PK collections. The ECG assessments will be performed before the PK sample is collected.
- ^c 24 hour sample collected on Cycle 1 Day 2 and Cycle 1 Day 6 (only for QD schedule).
- ^d Unless the last dose of study drug was administered > 1 week prior to the event (See Section 6.7).
- ^e PK samples will no longer be required after implementation of CSP Version 5.

All PK samples need to be collected within 10% of the nominal time (\pm 6 minutes for a 60 minute sample) to be protocol compliant. Pre-dose samples can be collected any time prior to dosing. The timing of the PK samples may be adjusted during the study, dependent on emerging data and in order to ensure appropriate characterization of the plasma concentration-time profiles.

If a patient misses any doses of AZD1775 a day prior to PK sampling, the Medical Monitor should be contacted as to any effect of the missed doses and potential changes required on the timing of the PK assessments. All other assessments, including laboratory safety assessments, vital signs and RECIST should continue to be performed as per study plan, relative to baseline assessments.

Samples will be collected, labelled, stored, and shipped as detailed in the Laboratory Manual.

PK samples will also be collected when imaging is performed for response assessment, at the time of AEs possibly related to AZD1775 (unless the last dose of study drug was administered > 1 week prior to the event), and at the end of treatment or at the time of progression.

5.4.2 Storage and destruction of pharmacokinetic samples

Pharmacokinetic samples will be disposed of after the Bioanalytical Report finalisation or six months after issuance of the draft Bioanalytical Report (whichever is earlier), unless requested for future analyses.

Any pharmacokinetic sample remaining after analysis for AZD1775 may be used for exploratory drug-drug interaction (DDI), metabolite, or biomarker analyses. Any results from such analyses may be reported separately from the CSR.

Pharmacokinetic samples may be disposed of or destroyed and anonymised by pooling. Additional analyses may be conducted on the anonymised, pooled PK samples to further evaluate and validate the analytical method. Any results from such analyses may be reported separately from the clinical study report (CSR).

Incurred sample reproducibility analyses, if any, will be performed alongside the bioanalysis of the test samples. The results from the evaluation will not be reported in the CSR but separately in a Bioanalytical Report.

Any residual back-up PK samples will be disposed of after the CSR is finalized.

5.5 Pharmacodynamics (PDx)

5.5.1 Repeat Biopsies

This study is designed in part to provide evidence of proof of mechanism (POM). For the Wee1 inhibitor AZD1775, this means to demonstrate that following treatment of patients there is a measurable decrease from baseline in readouts of activity of the Wee1 kinase.

The baseline Wee1 pharmacodynamic (PD) marker, pCDK1 (pCDC2), will be retrospectively assessed from the baseline biopsy. A post-treatment biopsy will then be taken after first dose on day 2 or day 3 of the first cycle of treatment.

These paired biopsies will be considered evaluable for POM if assessable by Immunohistochemistry (IHC) for the biomarker above and if the concurrent pharmacokinetic (PK) blood sample is consistent with the patient having had adequate pharmacological exposure to AZD1775.

We estimate that we would need at least 7 patients with evaluable paired biopsies in order to have confidence in an assessment of POM (see statistical calculations below).

A patient showing the target decrease of 50% or more (evaluated as number of cells showing positive staining in post vs pre dose) in pCDK1 will be considered a pharmacodynamic responder. This value is based on preclinical data correlating with anti-tumour efficacy, using the

same assay to be used on clinical samples. We have set a POM target value of 50% of patients having a pharmacodynamic response in their tumour biopsy. With n=7 biopsies, we would accept having established POM if 4 out the 7 biopsies show the desired biomarker change.

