- f Haematologic samples (2.7 mL) will be collected to measure complete blood count (CBC) with differential and platelets. Samples should be taken and reviewed prior to administration of AZD1775.
- g Clinical chemistry samples (2.7 mL) will be collected to measure BUN, creatinine, sodium, potassium, chloride, calcium, alkaline phosphatase (ALP), AST, ALT, total bilirubin, and albumin.
- h PT/INR/PTT will be obtained at baseline. Repeat beginning of every cycle if patient is on Coumadin.
- i Pregnancy tests will only be performed in women of childbearing potential at screening, within 3 days of study treatment, prior to the first dose of study treatment on Day 1 of each cycle, at the EOT visit and the FPV (see Section 3.8).
- j Patients are required to provide an archival tumour sample or fresh/recent tumour sample to participate in the study (see Section 5.6). Refer to the Laboratory Manual for additional information around sample requirements.
- k An on-treatment tumour biopsy is required for all patients with easily accessible lesions within 12 hours of one of the last AZD1775 doses taken on Day 4 or 5 or within the first 12 hours of Day 6 in Cycle 2 unless medically contraindicated on the scheduled day in the opinion of the investigator. The exact timing of the biopsy relative to the first dose of AZD1775 should be noted as described in the Laboratory Manual.
- l AZD1775 dosing compliance will be reviewed with the patient and documented at each visit. Dosing diaries will be collected at the beginning of each new cycle and at the end of treatment. The patient will be provided study medication to take home. Refer to Section 7.1 and 7.6
- m PK samples for AZD1775 non-food effect patients will be collected on Cycle 1 Day 1 and Cycle 1 Day 5 pre-dose and at 1 hour, 2, 4, 6, 8, 10 and 24 hours post-dose. On Cycle 5 Day 5, non-food effect PK samples will be taken pre-dose only and then pre-dose only every 3-5 cycles. Note: beyond the PK for Cycle 5 Day 5, collections will be flexible for staff and patient convenience, and the PK may be collected once every 3, 4 or 5 cycles (instead of every 4 cycles) on day 3, 4 or 5 (instead of day 5). All PK samples need to be collected within 10% of nominal time (± 6 minutes for a 60 minute sample). Details for processing, handling and shipping specimens are in the Laboratory Manual. PK samples will no longer be required after implementation of CSP Version 5.

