5.6.3 On-treatment tumour biopsy

An on-treatment tumour biopsy is required for all patients with surface accessible lesions within 12 hours of one of the last AZD1775 doses taken on Day 4 or 5 or within the first 12 hours of Day 6 in Cycle 2 (Day 4 through 6) unless medically contraindicated on the scheduled day in the opinion of the investigator. The exact timing of the biopsy relative to the first dose of AZD1775 should be noted as described in the Laboratory Manual. Studies may include, but are not limited to, analysis of the downstream effects of Wee1 inhibition such as changes in the levels of phosphorylation of the Wee1 kinase substrate CDC2.

For the Wee1 inhibitor AZD1775, this means to demonstrate that following treatment of patients there is a measurable decrease from baseline in readouts of activity of the Wee1 kinase via analysis of the levels of phosphorylated CDC2 (pCDC2) in tumour samples. The collection of baseline and on-treatment biopsies is essential to guarantee the comparison of pCDC2 levels before and during treatment and to provide evidence that patients receive a biologically active dose.

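### Proof of mechanism: Section 5.5.1 gives a biopsy time that conflicts with Section 5.6.3 and Tables 2-4, no concurrent PK sample is scheduled at the study-plan time, and the calculation behind the 4-of-7 rule is not shown

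*Protocol*

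**What the plan says.** Section 5.5.1 says the study is designed partly to show proof of mechanism, meaning a measurable fall from baseline in Wee1 kinase activity, read from phosphorylated CDK1 (CDC2) in paired biopsies.

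- **Biopsy time, Section 5.5.1:** "A post-treatment biopsy will then be taken after first dose on day 2 or day 3 of the first cycle of treatment".
- **Biopsy time, Section 5.6.3:** a 12-hour limit is set relative to "one of the last AZD1775 doses taken on Day 4 or 5 or within the first 12 hours of Day 6 in Cycle 2".
- **Biopsy time, study plan:** Table 2 footnote j and footnote k of Tables 3 and 4 agree with Section 5.6.3: "or within the first 12 hours of Day 6 in Cycle 2 unless medically contraindicated".
- **Evaluability, Section 5.5.1:** the marker must be assessable by immunohistochemistry, and a pair counts only "if the concurrent pharmacokinetic (PK) blood sample is consistent with the patient having had adequate pharmacological exposure to AZD1775".
- **PK schedule:** Table 3 footnote m states: "PK samples for AZD1775 non-food effect patients will be collected on Cycle 1 Day 1 and Cycle 1 Day 5 pre-dose", followed by post-dose times up to 24 h. Table 6 footnote c adds: "24 hour sample collected on Cycle 1 Day 2 and Cycle 1 Day 6 (only for QD schedule". Food-effect patients (Table 5) are sampled to 10 h on Cycle 1 Days 1 and 5 and Cycle 2 Day 1. The next scheduled sample in both tables is on Cycle 5 Day 5.
- **Rule, Section 5.5.1:** a responder has a fall of at least 50% in pCDK1, and the target is that 50% of patients respond. At least seven evaluable pairs are said to be needed, with a pointer to calculations further down. What follows is the rule: "we would accept having established POM if 4 out the 7 biopsies show the desired biomarker change".

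**The concern.** The paired biopsies are invasive, and Section 5.6.3 calls them essential to show that patients receive a biologically active dose. Three features of the text weaken what can be concluded from them.

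First, two current sections give different biopsy times for one comparison. A biopsy on Cycle 1 Day 2-3 follows two or three days of dosing at most. A biopsy on Cycle 2 Day 4 follows 5 + 4 = 9 dosing days on 5/9, 10 + 4 = 14 on 5/2 and 15 + 4 = 19 on 5/2 weekly. These are different exposures, and pairs from the two windows should not be pooled without a stated reason.

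Second, the evaluability condition relies on a sample that the PK schedule does not provide at the study-plan biopsy time. Applied literally, it would remove every pair collected as Tables 2-4 direct.

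Third, the number seven is presented as the result of a calculation that the reader cannot find. Nothing shows what 4 of 7 does or does not rule out.

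**Working it through.** **1. Biopsy time.** Section 5.5.1 names pCDK1 (pCDC2) and Section 5.6.3 names pCDC2. Section 1.2 gives CDK1 and CDC2 as the same protein, so the comparison is the same. Tables 2-4 have one on-treatment biopsy row, marked on Cycle 2 Days 4, 5 and 6. No table has a Cycle 1 biopsy.

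**2. Scheduled PK against each possible biopsy time** (Tables 2-6 and their footnotes).

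| Biopsy time | Non-food-effect QD | Food-effect, including BID |
|---|---|---|
| Cycle 1 Day 2 (5.5.1) | 24 h sample after the Day 1 dose | none |
| Cycle 1 Day 3 (5.5.1) | none | none |
| Cycle 2 Day 4-6 (5.6.3, Tables 2-4) | none | none |

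The one match is tied to the Day 1 dose, not to the biopsy, and falls at a time when no study-plan table has a biopsy.

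**3. The promised calculation.** The stated figures are n = 7, cut-off 4 and target 50%. No uninteresting rate, error rate, power or confidence level is given, so n = 7 cannot be reproduced. The cut-off can be read as the smallest count whose observed rate reaches the target: 4/7 = 57.1%, while 3/7 = 42.9%. The required n depends heavily on the missing input. Assuming 80% power at a true 50% and one-sided alpha of at most 0.10, an uninteresting rate of 10% needs n = 5 (cut-off 2), 20% needs n = 12 (cut-off 5) and 25% needs n = 19 (cut-off 8).

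**4. What the rule delivers**, reading 4 of 7 as at least 4:

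P(X ≥ 4) = Σ C(7,k) p^k (1−p)^(7−k), k = 4 to 7.

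At p = 0.5: (35 + 21 + 7 + 1)/128 = 64/128 = 0.500.

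At p = 0.2: 0.02867 + 0.00430 + 0.00036 + 0.00001 = 0.033.

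| True responder rate | 10% | 20% | 30% | 40% | 50% | 60% | 70% | 80% |
|---|---|---|---|---|---|---|---|---|
| P(rule met) | 0.003 | 0.033 | 0.126 | 0.290 | 0.500 | 0.710 | 0.874 | 0.967 |

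The chance of meeting the rule reaches 80% only at a true rate of about 65%. Read literally as exactly four, the probability at 50% is 35/128 = 0.273.

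**5. Precision of 4/7.** The exact (Clopper-Pearson) 95% limits are the 2.5% point of Beta(4, 4) = 0.184 and the 97.5% point of Beta(5, 3) = 0.901, that is 18% to 90%.

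**6. Distance of the Cycle 1 Day 5 profile from the study-plan biopsy.** On a 14-day cycle, Cycle 2 Day 4-6 is study day 18-20, which is 13 to 15 days after Day 5. On a 21-day cycle it is study day 25-27, which is 20 to 22 days after.

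**The case against.** A reader might infer that the assessment cannot be run at all. The documents do not support that. A non-food-effect QD patient biopsied on Cycle 1 Day 2 meets both the Section 5.5.1 timing and the PK condition. Section 5.4.1 also lets PK times be adjusted, and a sample triggered by an adverse event could coincide with a biopsy. What remains is that the adjustment clause is meant for characterising the concentration-time profile, the extra samples are tied to imaging, adverse events, end of treatment or progression, and nothing is planned at the study-plan biopsy time.

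A reader might also infer that the protocol claims 4/7 establishes a 50% response rate. It does not. It says POM would be accepted, 50% is a target value, and Section 8.4 rules out formal hypothesis testing. Nor does the 0.50 at a true 50% show that seven or four was badly chosen: any majority rule with odd n gives exactly that. The rule does discriminate, with 3% acceptance at a true 20% and 87% at 70%.

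It would equally be too strong to say that 4 of 7 excludes 20%. That holds only one-sided (3.3%), against a null the protocol never states, and the two-sided 95% interval includes 20%.

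The two sections might be meant to describe separate biopsies. In that case the Cycle 1 biopsy is missing from every study-plan table, and the text still needs correcting.

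The point about weight stands. POM is not among the objectives in Sections 2.1-2.3, the MTD rests on DLTs, and Tables 2-4 are closed to enrolment.

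**Conclusion.** The contradiction in biopsy time is certain and in current text. If the concurrent-PK condition is applied as written to biopsies taken as Tables 2-4 direct, no pair has a scheduled sample that makes it evaluable. This assumes that concurrent means the same day and counts scheduled samples only.

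The calculation supporting seven pairs is promised in the protocol itself and is absent, so this is not a detail left to an SAP. The figures rest on independent patients, a common responder rate across doses and schedules, and reading the rule as at least four. On that footing the rule is met half the time at the 50% target, and an observed 4/7 is compatible with rates from 18% to 90%. That is too wide to support a declaration that POM is established without qualification.

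Severity is low to moderate: the interpretation of the paired biopsies is affected, but the MTD and the listed objectives are not.

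**What to change.** 1. **Biopsy time.** Reconcile Section 5.5.1 with Section 5.6.3 and Tables 2-4 so that one window is stated throughout. If two biopsies were meant, say so and enter both in the tables.
2. **Evaluability.** Replace the concurrent-PK condition with one that the collected data can meet. One option is the Cycle 1 Day 5 profile together with dosing-diary confirmation (Section 7.6) of the doses before the biopsy. Call it a proxy and state its limits: on the study-plan timing it precedes the biopsy by two to three weeks, it does not reflect later dose changes or vomiting, and under Section 7.3 food-effect patients take the drug with meals throughout Cycle 2.
3. **Decision rule.** Replace the pointer to absent calculations with the operating characteristics in the table above, and write the cut-off as at least 4 of 7.
4. **Reporting.** Give the responder proportion with its exact 95% CI (18% to 90% for 4/7) instead of declaring POM established.

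The cost is protocol wording and one line of analysis, with no extra biopsies or blood draws. The downside is that exposure is judged by a proxy and the POM statement becomes less favourable.
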